If discrepancies are identified between parental report and source verification in more than 10% of these samples, then our team will perform a full verification of all 200 participants. Verification will be made by source documentation (e.g., sleep study reports) or verbal confirmation through telephone calls to primary care physicians.

Primary Outcomes:

We will be measuring adherence to detect improvement in: thyroid screening, celiac disease screening, sleep apnea testing, ophthalmology exams, and audiograms

- *Thyroid*: TSH should be checked annually beginning at age 1
- *Celiac disease*: if symptoms present, obtain tTG-IgA and total IgA annually
- *Sleep study*: performed by 4 years of age and, again, if symptomatic
- *Ophthalmology exam*: annually, ages 1-5; every 2 years, ages 5-13; every 3 years, ages 13-21; every 2 years, ages 21 and older
- *Audiograms*: annually up to age 21, every 2 years thereafter

The indication for 1, 2, 3, 4, or 5 evaluations for a given participant at the time of their PCP visit based on age, history, and symptoms will be collected prior to randomization as described in the "Baseline Assessment" section.

Secondary Outcomes:

We also want to determine whether the intervention improves quality of life as measured by the nationally validated PedsQL survey instruments.

Six summary scores will be derived from the two PedsQL instruments: measures of (1) psychosocial health, (2) physical health, and (3) an overall total score from the PedsQL 4.0 parent-proxy, standard Short Form 15 Generic Core Scales; and measures of (4) parental health-related quality of life, (5) family functioning, and an (6) overall total score from the PedsQL 2.0 Family Impact Module.

We will also measure the quality of experience with the intervention from parents and PCPs and identify ways that the *Caregiver Checklist* and *Primary Care Provider Plan* could best serve the needs of underserved patients with DS. For this assessment, rather than assuming we know which questions to ask to best assess their experience, we will engage our Parent/Caregiver and PCP WGs to help us pose relevant questions. Our expectation is that the assessments will ask for their level of satisfaction with the content and

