guidance offered by the *Caregiver Checklist* and *Primary Care Provider Plan*, similar to the voluntary questionnaire used in our preliminary study described above. We also anticipate including open-text responses solicited from caregivers and providers about their experience using the system.

Data Analysis Plan

Our primary analysis will compare the mean number of caregiver-reported evaluations completed within 7 months of the index PCP visit between the intervention and usual care arms. We will analyze the data using a generalized linear model assuming beta-binomial distributed counts of evaluations among those indicated with parameters estimated by maximum likelihood. We will confirm our inference using a permutation test by direct randomization of assigned treatment labels. Significant benefit will be declared if the mean number of recommended tests is greater among participants randomized to the intervention and a two-tailed p-value for the treatment comparison is less than 0.05. A significant effect of the intervention will be declared only if the permutation test concurs with inference from the beta-binomial regression as the permutation test makes no assumptions concerning the true distribution of the data. We will analyze longitudinal changes in our secondary outcome measures using a shared-baseline repeated-measures ANOVA for each of 6 quality of life outcomes derived from the two PedsQL instruments. Linear contrasts will be used to test for treatment-specific improvements over time. As a sensitivity analysis, we will also use simple two-group Wilcoxon ranksum tests to compare changes from baseline in each follow-up assessment individually. With 6 secondary outcomes, we will test each secondary outcome at alpha = 0.008 two-tailed to control for multiple comparisons.

For studies involving treatment or diagnosis, provide information about standard of care at Partners (e.g., BWH, MGH) and indicate how the study procedures differ from standard care. Provide information on available alternative treatments, procedures, or methods of diagnosis.

Not applicable

Describe how risks to subjects are minimized, for example, by using procedures which are consistent with sound research design and which do not unnecessarily expose subjects to risk or by using procedures already being performed on the subject for diagnostic or treatment purposes.

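### Does the primary success rule test the wrong quantity because it speaks of recommended tests rather than completed ones?

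*Combined protocol and SAP*

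**What the plan says.** The Data Analysis Plan describes the primary quantity in three ways within one paragraph.

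- The comparison: the analysis will "compare the mean number of caregiver-reported evaluations completed within 7 months of the index PCP visit between the intervention and usual care arms".
- The model: a generalized linear model "assuming beta-binomial distributed counts of evaluations among those indicated", fitted by maximum likelihood.
- The decision: "Significant benefit will be declared if the mean number of recommended tests is greater among participants randomized to the intervention", together with the condition that "a two-tailed p-value for the treatment comparison is less than 0.05".

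A permutation test that reshuffles treatment labels is to confirm the inference, and it has a veto: "A significant effect of the intervention will be declared only if the permutation test concurs with inference from the beta-binomial regression". Its statistic is not stated.

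Under Primary Outcomes, "The indication for 1, 2, 3, 4, or 5 evaluations for a given participant at the time of their PCP visit" is determined from age, history and symptoms and collected before randomization. Each participant's denominator is therefore a baseline characteristic.

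**The concern.** The direction condition omits the word *completed*. Two literal readings follow, and neither concerns the outcome.

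- If *recommended* means indicated by guideline at baseline, treatment cannot affect the quantity. In simulated trials with a true effect and a significant model result, the intervention arm failed to have the larger baseline mean in 51–54% of cases.
- If it means the recommendations that DSC2U generates, only the intervention arm receives them during the trial. The condition would be met automatically, and a significant result in the wrong direction could be called a benefit.

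A second worry is that the opening sentence speaks of a plain mean count while the model conditions on the number indicated. With 1 to 5 indicated, chance imbalance in the denominator adds noise to the mean count. If the permutation test used that count, its veto would discard power. One set of assumptions (200 participants, mean 3.2 indicated with SD 0.7–1.0, control completion 25–70% by test, person-level logit SD 0.8, odds ratio 1.85) gives about 82% power for the model alone and 69–74% with the veto. That is a loss of 8 to 13 points, with type I error near 3% instead of 5%. This is the trial's only rule for claiming success.

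**Working it through.** **Inputs.** From the documents: 200 participants randomized 1:1, two-tailed alpha 0.05, 1 to 5 evaluations indicated. The documents give no power, effect size, completion rates, overdispersion, dropout or distribution of the number indicated, so there is no power figure to reproduce. All of these are assumed below.

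**Step 1: what the p-value tests.** The p-value is the treatment comparison in the beta-binomial model, so the significance test concerns completion among indicated evaluations under any reading of *recommended*. The disputed clause supplies only the sign. In that model the expected count is the number indicated times the completion probability, so a mean count and a completion proportion are two summaries of one model. Because the number indicated is fixed before randomization, the raw difference in means is unbiased, only less precise.

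**Step 2: what the raw count costs, by formula.** Let m be the number indicated, p the completion probability, rho the within-person correlation and n the number per arm. Power is Φ(difference/SE − 1.96).

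- Variance of a raw count: E[m p(1−p)(1+(m−1)rho)] + p² Var(m).
- Variance of the model-based proportion: p(1−p) / (n E[m/(1+(m−1)rho)]).

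Example: m uniform on 1–5 (mean 3, variance 2), rho 0.2, n = 100, 40% against 52%.

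- E[m(1+(m−1)rho)] = 3 + 0.2×8 = 4.6.
- Raw count, control: 0.24×4.6 + 0.16×2 = 1.424. Intervention: 0.2496×4.6 + 0.2704×2 = 1.689. SE = √(3.113/100) = 0.1764. Difference = 3×0.12 = 0.36. Power = Φ(2.040−1.96) = 53%.
- Model: E[m/(1+(m−1)rho)] = (1 + 1.667 + 2.143 + 2.5 + 2.778)/5 = 2.017. SE = √(0.4896/201.7) = 0.0493. Power = Φ(2.436−1.96) = 68%.
- Raw count without the p² Var(m) term: SE = √((1.104+1.148)/100) = 0.1501. Power = Φ(2.399−1.96) = 67%.

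Nearly the whole gap is denominator noise, and a statistic that allows for the number indicated removes it.

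**Step 3: the joint rule, by simulation.** Beta-binomial data, 1,000 trials per scenario, likelihood-ratio test, 499 permutations; simulation error is about 1.5 points per power estimate. Power in % at 100 per arm, rho 0.2, 40% against 52%:

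| Number indicated | Model alone | Model and higher raw mean | Model and raw-count permutation | Model and permutation adjusted for number indicated |
|---|---|---|---|---|
| Centred on 3 | 70.1 | 70.1 | 57.1 | 66.8 |
| Uniform 1–5 | 67.2 | 67.2 | 48.2 | 62.8 |
| Bimodal | 64.2 | 64.2 | 40.6 | 58.5 |

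Across all 15 scenarios (80 or 100 per arm, rho 0.1 or 0.2, control completion 25–60%, gain 11–12 points):

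- Direction condition, read as completed tests: loss of 0 to 0.6 points.
- Agreement with a raw-count permutation: loss of 9.8 to 35.0 points.
- Agreement with an adjusted permutation: loss of 2.2 to 6.3 points.

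Under the assumptions listed with the concern, the adjusted version kept 81% of the model's 82%, with type I error of 4.6–4.8%.

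**Step 4: where any loss arises.** The direction wording causes essentially none. All material loss depends on permuting the raw count, which the plan does not say.

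**The case for a change.** The best case for a change is that a success rule should not depend on the reader supplying a word. *Recommended* is not a neutral term here, since the intervention itself consists of personalized recommendations. All ages are eligible and the number indicated depends on age, while randomization is stratified only on travel time and insurance, so nothing in the design balances the denominator. The only summary the plan names for the comparison is a mean number, so an analyst could permute it in good faith. Rewording would cost nothing and would remove a choice that might otherwise be made after seeing results.

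Two parts of this stand: the wording is inconsistent, and the permutation statistic is unstated. The rest is weaker.

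- Both literal readings contradict the paragraph's opening sentence, which sets the comparison on evaluations completed. They also contradict the trial's stated aim of adherence to guideline evaluations.
- The plan also names a likelihood-based model with a treatment parameter. A permutation test introduced to confirm that model's inference, because it makes no distributional assumption, is at least as naturally run on that parameter's statistic.
- The analyst's freedom is limited. The permutation test can only withhold a claim, so no choice of statistic can raise the false-positive rate above that of the beta-binomial test. The exposure is lost power, not a false claim of benefit.

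**Conclusion.** The concern does not call for a change. The primary test addresses the right quantity, and the direction wording is a slip whose meaning the same paragraph settles; read in context, it cost at most 0.6 points of power in any scenario examined. The unstated permutation statistic is a gap. With a statistic consistent with the model, the agreement rule costs little: about 1 point in one simulation and 2 to 6 in the other. A loss of about 10 to 35 points needs the raw count to be permuted, which the plan does not prescribe.

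The 8 to 13 point figure is not specific to this trial. It rests on assumed completion rates, effect size, overdispersion and distribution of the number indicated. The analytic loss for a raw count ranged from about 3 to 41 points as those assumptions varied.

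The conclusion rests on the analyst reading *recommended tests* as recommended tests completed, and on permuting a statistic that allows for the number indicated. Both follow from an ordinary reading of the plan.

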After submission of the Baseline Assessment, the parents/caregivers will be e-mailed a unique link to their DSC2U intervention form. The parent/caregiver will need to enter the month and day of birth of the person with Down syndrome to access their form. Using that information and their unique link, they can return to and complete the DSC2U form (Appendix H) at their convenience. Reminder e-mails to complete the DSC2U form will be sent at 4, 3, and 2 weeks prior to their son's/daughter's scheduled PCP annual well visit appointment. After they have completed DSC2U form, the system will send the parent/caregiver a link to their Caregiver Checklist (Appendix I) and Primary Care Provider Plan (Appendix J), which they will access by entering the month and day of birth of the person with Down syndrome. The DSC2U Caregiver Checklist and Primary Care Provider Plan will be accessible online until the end of the study period and may be downloaded and printed at the user's discretion.

Control Arm

After submission of the Baseline Assessment, parents/caregivers in the Control arm will be sent an e-mail message thanking them for their participation in the study. Included will be a reminder to let study personnel know if their son's/daughter's scheduled appointment with the PCP changes. Control arm participants will be receiving usual care—that is, the natural advice and recommendations that would be offered by their PCPs. (Upon conclusion of the RCT, control group participants will be offered the same Caregiver Checklist and Primary Care Provider Plan intervention.)

PCP Visit

Prior to each patient's scheduled PCP visit, the parent/caregiver will receive 2 reminders for their upcoming appointment, including a request to let our study personnel know if the date of the appointment has changed. Because the timing between study enrollment and scheduled PCP visit will vary among participants, we will plan to send these appointment reminders at approximately 4 weeks, then 1 week prior to the scheduled appointment.

Post-Visit Assessments (Both Intervention and Control Arms)

- Secondary outcome measures: PedsQL 2.0 Family Impact Module; PedsQL 4.0 parent-proxy, standard Short Form 15 Generic Core Scales (Appendix G)

In addition, with direct input from our Patient/Caregiver working group (WG) and PCP WG, we will be designing three novel surveys:

- Health Care Outcome Survey (for parents/caregivers) (for Primary Outcomes) (Appendix F)

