- Parent/Caregiver Experience Survey (for Secondary Outcomes) (Appendix K)
- Primary Care Provider Experience Survey (for Secondary Outcomes) (Appendix L)

Survey Implementation

The Experience Surveys (for both the parents/caregivers and PCPs) will be administered approximately 2 weeks after the PCP visit at Post-visit Assessment 1 (T1) (Figure 1). Parents/Caregivers will be invited by e-mail to complete their experience survey through REDCap. PCPs will receive their experience survey by mail, with an option to complete the survey electronically on REDCap. PCPs whose e-mails were provided by the parents/caregivers will also receive a direct invitation by e-mail to complete their survey. In order to minimize loss to follow-up, reminder e-mails will be sent 3 times about 2 weeks apart, concluding with a phone call in the eighth week by our study personnel. We certainly hope to maximize the PCP response rate, but our primary outcomes are not dependent on their responses.

Parents/Caregivers will be asked by e-mail to complete the Health Care Outcomes Survey through REDCap approximately seven months after the PCP visit at Post-visit Assessment 2 (T2) (Figure 1). In order to minimize loss to follow-up, reminder e-mails will be sent 3 times about every 2 weeks apart, concluding with a phone call in the 8th week by our study personnel.

[figure not shown]

Figure 1. Survey implementation at various points.

- **Baseline:** Health Care Outcome Survey, PedsQL 2.0 Family Impact Module and PedsQL 4.0 parent-proxy, standard Short Form 15 Generic Core Scales
- **T₀ (PCP Visit)**
- **T₁ (Post-visit Assessment 1):** PedsQL 2.0 Family Impact Module and PedsQL 4.0 parent-proxy, standard Short Form 15 Generic Core Scales, Parent/Caregiver Experience Survey, and PCP Experience Survey
- **T₂ (Post-visit Assessment 2):** Health Care Outcome Survey, PedsQL 2.0 Family Impact Module and PedsQL 4.0 parent-proxy, standard Short Form 15 Generic Core Scales

Validation Assessment

Ten percent of the respondents across both groups will be asked to validate their self-report by providing documentation of laboratory and procedural results. For example, if parents attest to thyroid checks being done for their

sons/daughters, they will be asked to send documentation of the primary outcomes (e.g. study report or physician sign off). These participants will also receive 3 reminder e-mails and a phone call every 2 weeks.

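### The covariance structure and contrasts of the quality-of-life model are not stated; an ordinary repeated-measures ANOVA fit would make the 7-month test too liberal if correlation falls with time

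*Combined protocol and SAP*

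**What the plan says.** The Secondary Outcomes section says "Six summary scores will be derived from the two PedsQL instruments". The list under Figure 1 places both instruments at baseline, T1 and T2. The Survey Implementation section sets T1 at "approximately 2 weeks after the PCP visit at Post-visit Assessment 1 (T1") and T2 at "approximately seven months after the PCP visit at Post-visit Assessment 2 (T2"). Baseline comes before the primary care visit, and the PCP Visit section says that "the timing between study enrollment and scheduled PCP visit will vary among participants"; it gives no range.

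The Data Analysis Plan models the scores "using a shared-baseline repeated-measures ANOVA for each of 6 quality of life outcomes derived from the two PedsQL instruments". It continues: "Linear contrasts will be used to test for treatment-specific improvements over time". On error control it says "we will test each secondary outcome at alpha = 0.008 two-tailed to control for multiple comparisons". Wilcoxon rank-sum tests of change from baseline, one follow-up at a time, are a sensitivity analysis.

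The document gives no covariance structure, sphericity correction or robust standard error for this model. It gives no contrast weights, and no PedsQL standard deviation or between-visit correlation.

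**The concern.** Repeated-measures ANOVA, in its ordinary sense, takes equal variances and a single correlation for all visit pairs. The schedule makes equal correlations doubtful. The gap from baseline to T2 equals the baseline-T1 and T1-T2 gaps added together, so if correlation declines with time, baseline-T2 is the weakest of the three and lies below their average. A fit that applies the average to every pair credits T2 with more information from baseline than it has, and its standard error is too small. Where baseline-T1 is stronger than average, the T1 standard error is too large.

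At stake is the 0.008 level, which was chosen to hold error across six outcomes. A chance quality-of-life difference at 7 months would be declared more often than planned, and a real one at 2 weeks could be missed more often.

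**Working it through.** **The plan's figure.** 0.05/6 = 0.0083, which rounds to 0.008, and 6 x 0.008 = 0.048. The split is correct. The question is whether each test keeps its 0.008.

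**Inputs from the protocol.** 200 caregivers randomized 1:1, so about 100 per arm; three assessments; 0.008 two-tailed, for which the normal critical value is 2.652.

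**Assumed, because the protocol is silent.** The correlations r01 (baseline-T1), r02 (baseline-T2) and r12 (T1-T2); equal variances; complete data; no treatment effect.

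**Formula.** Let rho be the mean of the three correlations. With one common correlation, the shared-baseline arm contrast at visit t is the difference in follow-up means minus rho times the difference in baseline means. True variance over model variance is

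V = (1 + rho² − 2·rho·r0t) / (1 − rho²),

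which exceeds 1 exactly when r0t < rho. The actual level is 2[1 − Φ(2.652/√V)].

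**Worked case, 0.80/0.50/0.55.** rho = 1.85/3 = 0.6167 and rho² = 0.3803.
- T2: V = (1.3803 − 0.6167)/0.6197 = 1.232; 2.652/1.110 = 2.389; level 0.017.
- T1: V = (1.3803 − 0.9867)/0.6197 = 0.635; 2.652/0.797 = 3.328; level 0.001.

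**Range.** The same formula at T1 and T2, with the average of both follow-ups alongside:

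| r01 / r02 / r12 (assumed) | T1 | T2 | Average |
|---|---|---|---|
| 0.60 / 0.60 / 0.60 | 0.008 | 0.008 | 0.008 |
| 0.60 / 0.50 / 0.50 | 0.005 | 0.010 | 0.006 |
| 0.70 / 0.60 / 0.60 | 0.004 | 0.010 | 0.005 |
| 0.70 / 0.60 / 0.65 | 0.005 | 0.012 | 0.008 |
| 0.75 / 0.55 / 0.60 | 0.002 | 0.014 | 0.005 |
| 0.80 / 0.50 / 0.55 | 0.001 | 0.017 | 0.004 |
| 0.60 / 0.50 / 0.70 | 0.008 | 0.015 | 0.018 |

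**Lead time.** Now let correlation decay exponentially, reaching 0.5 to 0.8 at six to seven months, with or without a ceiling of 0.85, and let baseline precede the visit by 0 to 6 months. T2 then lies between about 0.011 and 0.027. T1 lies between practically 0 and 0.006; at a 6-month lead it is about 0.004 to 0.006. The average contrast runs from about 0.001 with no lead to about 0.016 at 6 months. A classical pooled-error ANOVA on changes, with V = (1 − r0t)/(1 − rho), gives somewhat larger T2 values: 0.020 in the worked case.

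**Simulation.** With 100 per arm and 60,000 null trials per set, the common-correlation fit rejected at T1 / T2 in 0.0008 / 0.016 (0.80/0.50/0.55), 0.0022 / 0.014 (0.75/0.55/0.60) and 0.0039 / 0.011 (0.70/0.60/0.60). A shorter run of 20,000 trials gave 0.013 at T2 for the first set. With an unstructured covariance, the level stayed between 0.007 and 0.010 at both visits in every run.

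**The case against.** The strongest reply is that the defect is inferred. The text never mentions a common correlation. A classical univariate ANOVA does not usually force the arms to share a baseline mean, so the shared-baseline label may point to a constrained longitudinal model, which can be fitted with an unstructured covariance. That stands, and it makes the point conditional.

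Further points stand in part:
- **Size.** Every correlation is assumed. A reader might infer that the error at T2 is simply doubled. In the table only the 0.80/0.50/0.55 set does so; the other sets with unequal correlations give about 1.2 to 1.9 times 0.008, and equal correlations give no inflation.
- **T1.** A reader might infer that the 2-week test is far too strict. T1 follows the primary care visit by 2 weeks, not baseline. With a 6-month lead the two gaps are each about 6.5 months, and the loss is modest.
- **Contrast.** An average of the two follow-ups would be conservative in several sets and liberal in others.
- **Familywise error.** Six tests at 0.017 give 6 x 0.017 = 0.102, but that is only an upper bound. The six scores include totals and components of the same instruments, so they should be positively correlated and the true figure lower.
- **Wilcoxon tests.** They need no common correlation and could expose a discrepant T2 result. But they are a sensitivity analysis, and no rule requires them to agree before a quality-of-life claim. The primary outcome does have such a rule, through its permutation test.

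**Conclusion.** The plan leaves the covariance structure and the contrasts open, and the ordinary meaning of the method it names would not hold 0.008 on this schedule if correlation falls with time. Under that fit, T2 is too liberal in every case tried with declining correlation, because baseline-T2 is the longest gap whatever the lead time. The size, about 0.010 to 0.027, rests on assumed correlations, equal variances and complete data. At T1 the level is between near 0 and about 0.006 for leads of up to 6 months.

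The documents do not support a flat statement that the quality-of-life error rate is doubled at 7 months, or that the trial's familywise error is 10%: neither the common correlation nor the correlations behind those figures is in the text. The primary analysis is untouched. The change is worth making because it is nearly free and settles the level whichever fit was intended.

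**What to change.** In the Data Analysis Plan, replace the repeated-measures ANOVA with a likelihood-based mixed model for each PedsQL score: one baseline mean common to both arms, visit as a category, an unstructured 3 x 3 covariance matrix, REML with Kenward-Roger degrees of freedom, and every available assessment included. Name the arm contrasts at T1 and at T2, and say which of them is tested at 0.008 for each score; if both are, say how the level is shared between them.

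The cost is wording and four more covariance parameters: three variances and three covariances instead of one variance and one correlation (6 − 2 = 4). With 200 families that is negligible. No change to data collection or sample size is needed.
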